## 1. SYNOPSIS

Name of Sponsor Company: CoLucid Pharmaceuticals, Inc.		Drug Under Study: Lasmiditan (COL-144)
Title of Protocol: A Study of Three Doses of Lasmiditan (50 mg, 100 mg and 200 mg) Compared to Placebo in the Acute Treatment of Migraine: A randomized, double-blind, placebo-controlled parallel group study (SPARTAN)		
Protocol Number: COL MIG-302	Phase: 3	Indication: Migraine - Acute Treatment

Primary Objective: To evaluate the efficacy at 2 hours of lasmiditan 50 mg, of lasmiditan 100 mg and of lasmiditan 200 mg compared to placebo on migraine headache pain and the Most Bothersome Symptom (MBS), as identified by the individual from the associated symptoms of nausea, phonophobia and photophobia.
 
Secondary Objectives: To explore the time course and effect of lasmiditan 50 mg, of lasmiditan 100 mg and of lasmiditan 200 mg on relief of pain and on the MBS.
 
Additional Objectives: To explore the effect and time course of a second dose of lasmiditan 50 mg, of lasmiditan 100 mg and of lasmiditan 200 mg compared to placebo on relief of pain and MBS when used for rescue and for recurrence of migraine. To explore resource utilization during the study compared to pre-study in terms of cardiovascular events and in terms of migraine episodes.
 
Safety Objective: To explore the safety and tolerability of lasmiditan 50 mg, of lasmiditan 100 mg and of lasmiditan 200 mg, as the first dose and as a second dose, in terms of adverse events (AEs), physical examinations, vital signs, clinical laboratory evaluations, and 12-lead electrocardiograms (ECGs).
		

Study Endpoints
 
Primary Endpoint: The proportion of subjects headache pain free at 2 hours post dose (defined as moderate or severe headache pain becoming none)
 
Key Secondary Endpoint: The proportion of subjects who are MBS free at 2 hours post dose (defined as the associated symptom present and identified as MBS prior to dosing being absent at 2 hours).
		

Study Design: This is a prospective randomized, double-blind, placebo-controlled study in subjects with disabling migraine (Migraine Disability Assessment (MIDAS) score <math>\geq 11</math>). Subjects will be stratified (yes or no) for use of concomitant medications that reduce the frequency of migraine episodes.
 
Subjects will be asked to treat a migraine attack with study drug on an outpatient basis. Subjects will be provided with a dosing card containing a dose for initial treatment and a second dose to be used for rescue or recurrence of migraine. Each subject's study participation will consist of a screening visit (Visit 1) with a telephone contact within 7 days to confirm eligibility, a Treatment Period of up to 8 weeks, and an End-of-Study (EoS) visit (Visit 2) within one week (7 days) of treating a single migraine attack. The total time on study is approximately 11 weeks.
 
At the Screening visit (Visit 1) subjects will provide written informed consent and authorize Health Insurance Portability and Accountability Act (HIPAA). Study eligibility will be assessed on the basis of medical history including migraine history, baseline physical examination (including height and weight), vital signs, clinical laboratory tests, 12-lead ECG and responses to the MIDAS questionnaire. Subjects will be asked about any concomitant medication use as well as any cardiovascular (CV) events in the last 6 months and/or related resource utilization such as visits to cardiologists, procedures, hospitalizations, new treatments or treatment
		

adjustments for CV disease. A Columbia Suicide Severity Rating Scale (C-SSRS) will be completed. Subjects will be given an electronic diary and be trained on its use to record information about their migraine, dosing their migraine and post-dose assessments. Subjects will be randomized, dispensed study drug and instructed not to treat an attack until their eligibility has been confirmed by telephone once all screening evaluations are complete. Subjects will be randomly assigned to one of 7 treatment sequences to receive lasmiditan 50 mg (L50 mg), lasmiditan 100 mg (L100 mg) or lasmiditan 200 mg (L200 mg) or placebo (P) for the first dose (in a 1:1:1:1 ratio) and the second dose, if needed for rescue or recurrence of migraine as follows:

First dose for treatment of migraine	Second dose for rescue or recurrence of migraine (if needed)
L50 mg	L 50 mg
	L 50 mg
	placebo
L100 mg	L100 mg
	L100 mg
	placebo
L200 mg	L200 mg
	L200 mg
	placebo
placebo	placebo

**Telephone Contact:** Within 7 days of **Visit 1** a phone contact must be made by study staff to the subject confirming eligibility in the trial. The subject will be reminded on the use of the diary and on dosing a migraine with study drug. Once eligibility is confirmed, subjects will begin the **Treatment Period**. Subjects considered not eligible will be advised not to take the study drug and an appointment for an **EoS/Visit 2** and the collection of study drug and the diary will be scheduled within one week (7 days) of the confirmation of eligibility phone call.

- **Treatment Period:** Subjects will be asked to treat their next migraine attack within 4 hours of onset providing that the headache severity is at least moderate at that time and not improving. Subjects will record their response to the first dose over the next 48 hours using an electronic diary. Subjects will be asked not to use rescue medication until at least 2 hours after dosing with study drug and completing the 2 hour assessments. If the migraine does not respond at 2 hours, a second dose of study drug may be taken up to 24 hours after the first dose as long as no other rescue medication has been used. If the migraine does respond within 2 hours (headache becomes pain free) but then recurs after 2 hours a second dose of study drug may be taken up to 24 hours after the first dose. Subjects will record their response to a second dose, taken for either rescue or recurrence, for 48 hours in the electronic diary. The total time for recording response to study drug is up to 72 hours depending on whether or not a second dose is used. Subjects are to contact the clinic to schedule **EoS/Visit 2** within one week (7 days) after 1 attack has been treated, or after 8 weeks have passed without treating an attack. The total time on study is approximately 11 weeks.

**Subject Population:** Adult patients with a history of migraine with or without aura.

[figure not shown]
**Number of Subjects:** Approximately 2968 subjects screened and randomized (742 per treatment arm based on the first dose) to ensure that at least 2280 subjects (570 per treatment arm based on the first dose) complete the Treatment Period

**Number of Centers:** Up to 150 centers in the US and rest of world (Western EU, )

**Test Product and Doses:** lasmiditan 50 mg, lasmiditan 100 mg; lasmiditan 200 mg and matching placebo

**Route of Administration:** Oral

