### 9.1.7 Dosing Instructions

Study drug should be administered as the **FIRST** treatment for an acute migraine attack. If the subject has already taken any prior analgesic or acute migraine treatment, he/she is no longer eligible to treat the current migraine attack but may treat a later attack with the study drug.

Subjects will be asked to treat their migraine attack within 4 hours of onset providing that the headache severity is at least moderate at that time and not improving. Subjects will record their response over the next 48 hours using an electronic diary. Subjects will be instructed not to use rescue medication until at least 2 hours after taking study drug. If the subject does not become headache pain free within 2 hours, rescue medication will be permitted after completion of the 2 hour assessments. A second dose of randomized study drug may be taken up to 24 hours after the first dose as long as no other rescue medication has been used. The Investigator will advise each subject as to alternative suitable rescue medication. Triptans, ergots, opioids and barbiturates **MUST NOT** be used for rescue medication within 24 hours of study drug administration. If the migraine responds within 2 hours (headache becomes pain free) but then recurs after 2 hours a second dose of randomized study drug may be taken for up to 24 hours from the first dose.

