### 10.5.1 Primary Analysis

The treatment effect between lasmiditan and placebo will be tested first for the primary endpoint of the proportion of subjects who are headache pain free and the key secondary endpoint of the proportion of subjects who are MBS free at 2 hours in the mITT population between the lasmiditan 200 mg and placebo dose group based on the first dose. The primary analysis will be completed using logistic regression Wald Chi-square test with a basic model including treatment group and region, using a one-sided test at the  $\alpha=0.025$  level of significance.

If the primary analysis is statistically significant (one-sided,  $p<0.025$ ), additional confirmatory hypotheses will be tested on the proportion of subjects who are headache pain free and the proportion of subjects who are MBS free at 2 hours in the lasmiditan 100 mg and placebo

groups followed by the lasmiditan 50 mg and placebo groups.

Headache pain free at 2 hours will be defined as a reduction in headache severity from moderate (2) or severe (3) at baseline to none (0) two hours after dosing with study drug. MBS free at 2 hours will be defined as a 'no' response to the presence of the symptom (either nausea, phonophobia, or photophobia) that was identified as MBS at predose, 2 hours after dosing with study drug.

A qualifying migraine is defined as a migraine treated with study drug within 4 hours of onset.

Subjects taking rescue medication within the first two hours or who fail to record headache severity at 2 hours will be assumed to have no headache response in the mITT and the ITT analyses.

A subject is defined to have used rescue medication within the first two hours post dosing if at least one medication is documented in the rescue medication log in the subject electronic diary for which:

$0 \text{ (min)} < \text{date/ time rescue medication (diary)} - \text{date/ time of dosing (diary)} < 120 \text{ (min)}.$

Subjects who do not provide a headache pain severity rating at baseline or who use other medication prior to the study drug for the study migraine attack will be assumed to have no headache response for the ITT analysis.

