 - The time intervals are 30 minutes, 1 hour, 1.5 hours, 2 hours, 3 hours, 4 hours, 24 hours, and 48 hours after the first dose of study medication. The e-diary sets the post dose assessments based on the recorded time of dosing. A subject that begins reporting their migraine at the exact time of dosing will have all of the post dose assessment time points available to them. If a subject starts recording their information in the e-diary after they dose including the time of dosing, the assessments that become available for them are based on the time of dosing, relative to when they accessed the e-diary. For example, if at 1-hour post actual dosing the subject initiates migraine mode and begins entering data into the e-diary, the subject will be allowed to respond to the initial questions about their migraine and time of dosing and then based on the time they record for dosing they automatically will miss subsequent time points, i.e.; the 30 minute and 1-hour time points. A missed time point is missed.
 - Alarms occur at the predefined time points to remind the subject it is time to complete the assessments. The Migraine Questions button is always available, but the subject is not be able to answer the questions until prompted by an alarm within a study migraine.
- Migraine Mode – Second Dose (Optional)
 - The subject should only take a second dose of study medication if the migraine pain is not gone by two hours after the first dose or the migraine pain was gone and came back two hours or more after the first dose (up to 24 hours after first dose).
 - The Dose 2 button will appear AFTER the e-diary recognizes 2 hours have passed since the first dose and remains until the 24-hour time point.
 - During the 2-hour post dose assessment the subject will be asked to indicate if he/she would like to take a second dose of study medication
 - If a second dose is reported alarm intervals are the same as for the reporting of the first dose and any remaining alarms from the first dose are cancelled. However, if

the subject inadvertently enters a dosing time of the second dose occurring prior to the first dose the first dose alarms do not stop and subject can therefore response to post-dose assessments based on time of dosing of first dose, therefore not really assessing their response to the second dose.

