5.4 Derivation of Electronic Diary Assessment Times for Efficacy and Exploratory Analysis

Primary and secondary efficacy endpoints along with second-dose exploratory analysis endpoints will be summarized at various elapsed times following dosing. The endpoints will depend on data collected by an e-diary that requires a subject's response entries in the correct order and at the expected, scheduled assessment times. These assessment times are calculated by the e-diary from elapsed time since dosing. (They will not be recalculated as a part of analysis programming.) The e-diary poses questions to be answered within a pre-specified window of elapsed time after dosing. There will be some scenarios when responses appear to have been limited by the e-diary programming, if questions are not answered in the expected order or during the programmed window, which may cause unscheduled data at some time points.

Unscheduled data can be defined as invalid data at time points which do not correspond to the actual dosing data at the intended time point entered by subject. Listed are some examples of unscheduled data:

1. When subject takes 2nd dose but due to subject's response to the timing of dosing question in e-diary, the e-diary does not understand that subject took 2nd dose, but continues to collect the first dose time points because they are still 'valid' based on subject's entry. Thereby second dose questions do not become available until the time points align. In this case, the data for first dose is unscheduled.
2. Due to subject's responses to e-diary questions, e-diary assumes that subject took 2nd dose at one-time point but subject indicates dosing at a different time point. This makes their second dose data unscheduled but often keeps first dose data from being unscheduled.
3. Due to subject's responses to e-diary questions, e-diary assumes that subject took 2nd dose but subject indicates not dosing as per study drug accountability and CRF confirmation so 2nd dose data will be unscheduled.

Some specific scenarios are listed below for derivation of analysis time points for efficacy and exploratory endpoints.

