11.2 Primary Efficacy Analysis

The primary efficacy analysis will test the treatment effect, between lasmiditan 200 mg and placebo, of the primary efficacy endpoint of the proportion of subject's headache pain-free at 2 hours post-dose. This analysis will be presented by treatment group, based on the first dose.

Headache pain-free is defined as a reduction in headache severity from mild (1), moderate (2), or severe (3) at baseline to none (0).

Subjects who do not provide a headache pain severity rating at baseline, or who do not provide a headache pain severity rating at the two-hour time point will be assumed to have not achieved headache pain-free.

Subjects taking any rescue medication within the first two hours will be assumed to have not achieved headache pain-free. Subjects who use other medication prior to the study drug to treat the migraine attack will also be assumed to have not achieved headache pain-free.

Subjects who treat a no (0) severity migraine will not be included in the primary analysis. Sensitivity analyses, as described in Sections 11.4, 11.5 and 11.6 will also be performed for the primary endpoint on the mITT population.

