11.3 Key Secondary Efficacy Analysis

The key secondary efficacy analyses will test the following:

- The treatment effect, between lasmiditan 200 mg and placebo, of the key secondary efficacy endpoint of MBS-free at 2 hours post-dose.
- The treatment effect, between lasmiditan 100 mg and placebo, of the key secondary efficacy endpoint of headache pain-free at 2 hours post-dose.
- The treatment effect, between lasmiditan 100 mg and placebo, of the key secondary efficacy endpoint of MBS-free at 2 hours post-dose.
- The treatment effect, between lasmiditan 50 mg and placebo, of the key secondary efficacy endpoint of headache pain-free at 2 hours post-dose.
- The treatment effect, between lasmiditan 50 mg and placebo, of the key secondary efficacy endpoint of MBS-free at 2 hours post-dose.

MBS-free is defined as the absence of the associated symptom of migraine (either nausea, phonophobia, or photophobia) at 2-hour post-dose that was identified pre-dose as the most bothersome symptom. Subjects who record that no symptoms were present at baseline will be

excluded from the key MBS analyses. Likewise, subjects who treat a migraine of no (0) severity will not be included in the key analysis of headache pain. Such subjects will also be excluded from the table produced for the sensitivity analysis described in Section 11.5, but not from the programming steps that impute missing MBS data.

Subjects who do not provide a symptom rating at baseline will be considered as follows:

- Subjects who record at least one symptom present at baseline, but who do not designate one as most bothersome, will be treated as if all symptoms present are most bothersome and will be considered MBS-free at any time point post-dose only if all symptoms present at baseline are no longer present at that time point.

Subjects taking rescue medication within the first two hours, or who fail to record a symptom rating at 2 hours, will be assumed to have not achieved MBS-free. Subjects who use other medication prior to the study drug to treat the migraine attack will also be assumed to have not achieved MBS-free.

The counts and percentages of which symptom was chosen as the most bothersome symptom will also be presented.

These analyses will be presented by treatment group, based on the first dose.

Sensitivity analyses, as described in Sections 11.4, 11.5 and 11.6 will also be performed for the key secondary endpoints on the mITT population.

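### The early-rescue scoring rule stops at 2 hours after dosing and does not reach the 2-hour rating, so a non-study rescue drug taken in between is not scored as failure

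*Protocol*

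**What the plan says.** **Conduct.** The synopsis, protocol 5.5 and SAP 2.1 ask subjects "not to use rescue medication until at least 2 hours after dosing with study drug and completing the 2 hour assessments". Protocol 9.1.7 has a sentence with the time condition alone ("Subjects will be instructed not to use rescue medication until at least 2 hours after taking study drug"), but its next sentence, like protocol 7.3.1, allows rescue only once the 2-hour assessments are done.

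**Scoring.** Protocol 10.5.1 begins its definition "A subject is defined to have used rescue medication within the first two hours post dosing if at least one medication is documented" and ends it with a strict upper limit: "date/ time of dosing (diary)} < 120" minutes. SAP 11.2 says "Subjects taking any rescue medication within the first two hours will be assumed to have not achieved headache pain-free". SAP 11.3 does the same for MBS, naming "Subjects taking rescue medication within the first two hours, or who fail to record a symptom rating at 2 hours". Step 1 of the multiple-imputation analysis in SAP 11.5 uses the same period.

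**Diary.** SAP 5 states that "the subject is not be able to answer the questions until prompted by an alarm within a study migraine". SAP 5.4 adds: "The e-diary poses questions to be answered within a pre-specified window of elapsed time after dosing". Neither gives the width of the window.

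**Related provisions.** SAP 8.5 tabulates other migraine medication as taken before or after the 2-hour assessment. SAP 11.7.10 identifies rescue by a second study dose or by a positive answer to the diary question on other medication since the migraine began. Neither is linked to the confirmatory endpoints.

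**The concern.** The conduct rule keeps the 2-hour rating free of other treatment by tying rescue to completion of that rating. The scoring rule is tied to the clock alone. Because the rating cannot precede the alarm, it normally falls at or after 120 minutes, which leaves an interval between the end of the scoring rule and the rating that decides the endpoint. Relief from another drug taken in that interval would be credited to the randomized first dose.

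The rule applies to 2-hour pain-free and MBS-free for all three doses, so all six tests in the SAP 11.1 hierarchy depend on it. The missing-data analysis in SAP 11.5 repeats the same limit and would not show the effect.

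**Working it through.** **1. Timing**

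- Rescue scored as failure: more than 0 and less than 120 minutes after dosing (protocol 10.5.1).
- Earliest 2-hour rating: the 2-hour alarm, about 120 minutes (SAP 5).
- Latest rating: the end of a window of unstated width (SAP 5.4).
- Uncovered interval: from 120 minutes to the actual rating. Its length cannot be computed from the documents.

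**2. Does another rule close the interval?**

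- *Second study dose: yes, by inference.* SAP 5.2 ends first-dose data at the second dose, and SAP 5 cancels the remaining first-dose alarms once a second dose is reported. The rating should then be missing, and SAP 5.3 counts a missing rating as non-response.
- *Non-study drug: no.* SAP 11.2 and 11.3 have no rule for it beyond the first two hours.
- *Per-protocol set: unclear.* SAP 4.2 excludes rescue before the 2-hour time point. That may mean 120 minutes or the diary assessment itself.
- *MBS.* The explicit formula in protocol 10.5.1 is attached to headache response. For MBS the basis is the wording of SAP 11.3.

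**3. The plan's own power figure**

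Inputs from protocol 10.1: 570 per arm, one-sided 0.025, pain-free 7.4% on placebo and 18.8%, 13.6% and 13.9% on 200, 100 and 50 mg.

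Power = Φ[(d − 1.96·SE0)/SE1], where SE0 = √(2·p̄(1−p̄)/n) and SE1 = √([p1(1−p1) + p2(1−p2)]/n).

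For 100 mg: d = 0.062, SE0 = 0.01816, SE1 = 0.01807, so power = Φ(1.46) = 92.8%. The same formula gives 99.99% for 200 mg and 94.6% for 50 mg. The stated figure of more than 90% is reproduced and is not disputed.

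**4. Illustration of size**

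Let g be the share of true non-responders who take a non-study drug in the interval and are then scored pain-free. The observed rate is p′ = p + g(1 − p). With equal g in both arms, the difference becomes (1 − g)·d. The documents give no value for g, so every value below is an assumption. At g = 1%, the number miscredited per 570 is 0.01 × 0.926 × 570 = 5.3 on placebo and 0.01 × 0.864 × 570 = 4.9 on 100 mg.

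| g placebo | g 100 mg | Placebo rate | 100 mg rate | Difference (points) | Power |
|---|---|---|---|---|---|
| 0 | 0 | 7.40% | 13.60% | 6.20 | 92.8% |
| 0.1% | 0.1% | 7.49% | 13.69% | 6.19 | 92.6% |
| 0.5% | 0.5% | 7.86% | 14.03% | 6.17 | 91.7% |
| 1% | 1% | 8.33% | 14.46% | 6.14 | 90.4% |
| 2% | 2% | 9.25% | 15.33% | 6.08 | 87.9% |
| 2% | 1% | 9.25% | 14.46% | 5.21 | 77.8% |
| 1% | 2% | 8.33% | 15.33% | 7.00 | 95.6% |

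With no true effect (7.4% in both arms), the one-sided error stays at 0.025 for equal g. It is about 0.006 if placebo has 2% and lasmiditan 1%, and about 0.080 if the split is reversed. The unequal rows show that the net direction depends on the split between arms, on which the documents are silent.

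**The case against.** The strongest reply is that the SAP does not fix a 120-minute clock. It does not repeat the protocol formula. Its only worked definition of rescue use, in 11.7.10, relies on a diary answer, and a subject who took a drug at 125 minutes and reported it at the 2-hour assessment would be flagged. This largely stands: the SAP leaves its two-hour phrase undefined and does not positively exclude the interval. But 11.7.10 is exploratory, 11.2 and 11.3 do not refer to it, and the only explicit formula for the endpoint is the protocol's.

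The interval is also bounded. A missed assessment cannot be completed later, and a missing rating is non-response. To be miscredited, a subject must act against the instruction, become free of pain or of the MBS, and still answer inside the window. Triptans, ergots, opioids and barbiturates are barred as rescue for 24 hours (protocol 7.3.1). This stands too and is why the effect is probably small.

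A reader might infer that the gap favours lasmiditan. The documents do not support that: it is open in every arm, equal shares dilute the difference, and no information exists on unequal shares. Nor can it be said that the per-protocol analysis certainly shares the gap, since the SAP 4.2 wording can be read either way.

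Finally, minute-level comparison of time stamps would be fragile. SAP 4.2 notes that CRF medication records carry dates without times, and SAP 5.4 describes retroactive and future-dated diary entries. This stands and shapes the fix.

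**Conclusion.** The mismatch between conduct and scoring is real for non-study rescue medication and affects both 2-hour endpoints. Its frequency, the length of the interval and the net direction cannot be determined from the documents. With equal shares of 0.1% to 2%, the 100 mg difference shrinks by 0.01 to 0.12 points and its power moves from 92.8% to between 92.6% and 87.9%. These shares are illustrative and the lower values are the more plausible, so the power figures are not evidence of a material loss. The 200 mg comparison is barely touched: 99.96% at an equal 2%. The MBS effect was not quantified. This is an inexpensive improvement to the endpoint definition, best settled before unblinding. It is not a defect that threatens the trial's conclusions.

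**What to change.** In SAP 11.2, 11.3 and step 1 of 11.5, and for clarity in 4.2, replace the two-hour cut-off with the plan's own reference point. Any other migraine medication reported as taken before the 2-hour assessment should count as not pain-free and not MBS-free. The main derivation should be a positive answer, at or before the 2-hour assessment, to the diary question used in 11.7.10. The diary rescue time should support it where recorded. Keep the existing handling of a second study dose.

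Note the departure from the protocol 10.5.1 formula in SAP 5.1, and state the width of the 2-hour response window so that the remaining uncertainty can be judged.

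The cost is a sentence in each section and one derivation from diary data already planned. A few subjects may move from responder to non-responder. Neither the instructions to subjects nor the rescue rules change.
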